Data collection will be entered into REDCap by [name] (Psychiatry Intake Coordinator) and reviewed by the PI or sub-investigator. [name], a VT Psychology graduate student, will be the data manager for the project. Thus, we request that she have access to REDCap data, without PHI access.

Data in REDCap that would be visible to [name] at VT would be:

subject number
randomized group (no intervention or minimal intervention)
date of assessment by [name] will be put as day 1 NOT a specific date of appointment
PHQ-9, GAD-7, BASE-6, USAUDIT, DAST-10 scores

Covid Event Checklist (positively checked answers with respect to COVID infection, prevention, negative mental health effects of Covid, SDOH and resiliency factors) - there are no dates or identifying information in this checklist, simply the check-marked items themselves
Adult Behavioral Health Screen (ABHS) (marked as completed or not)

The VT collaborator would not have access to any of the 18 HIPAA identifiers.

Data from REDCap will be exported to SPARC by HART and de-identified to allow other non-Carilion study members ([name]) to analyze data that is de-identified.

10.0

Human Subjects Research Description

10.1 In the opinion of the Principal Investigator, does this research impart minimal risk or greater than minimal risk to subjects?

As defined by regulation, minimal risk means that the probability and magnitude of harm or discomfort anticipated in the research are not greater in and of themselves than those ordinarily encountered in daily life or during the performance of routine physical or psychological examinations or tests. Please note that the IRB makes the final determination of risk level and may ask you to change this based on their decision.

If this is a Conversion of a Paper Application, select the risk level that has been determined already by the IRB at most recent review per the most recent approval letter (expedited review = minimal risk, full board review = greater than minimal risk).

- Minimal Risk
- Greater than minimal

10.3 Select ALL the types of research activities that will be involved in your human subject research subject, or select None.

- Drugs, biologics or other FDA-regulated products (other than devices)
- Medical devices
- Review of data/records (i.e. prospective clinical data collection from medical records, reviewing previously collected data)
- Biospecimen collection (i.e. blood, tissue, urine, saliva)

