CC-P&BM currently has a wait-list of over 300 adults referred for mental health evaluation and treatment. Access to psychiatric clinicians remains insufficient despite increasing numbers of providers in our clinic and the mental health needs associated with the pandemic are rising. As a result, a clinical intake coordinator (Licensed Professional Counselor) began in the CC-P&BM ambulatory clinic September 2021. This coordinator will individually contact people on the wait-list for psychiatric care by phone as part of routine care, beginning with the referrals most remote in time. The coordinator will complete an intake assessment for each wait-list individual who wants a psychiatric referral. Prior to the initial intake assessment by the intake coordinator, wait-list individuals will receive a bundle of PROMs automatically (through Owl Insights) to complete. These measures include the PHQ-9, GAD-7, BASE-6, DAST-10, USAUDIT, Covid Event Checklist and the Adult Behavioral Health Screen (ABHS), all of which are currently used in routine ambulatory care. The intake coordinator will complete the intake assessment, noting the completion, and scores of, the PROMs. Scores of the PHQ-9, GAD-7 and BASE-6 will be utilized to triage the most severe referrals and move them up for a sooner appointment (the triage system of scores and Nurse-Practitioner vs Medical Doctor screening questions are attached to this application). Any concern about patient safety is also addressed immediately during this intake and is also noted in the materials attached to this application. **Up to this point, all intake coordinator/referral interaction are part of routine care.**

If eligible and capable of consent based on intake coordinator clinical judgement, individuals will then be randomized to participate to the no intervention group (completion of screening PROMs only during the intake coordinator assessment) or the minimal intervention group (intake coordinator assessment, including PROM screening and then prospective monthly PROM completion in addition to assigned microlearning

patient education videos). We will analyze changes in PROM scores for individuals engaged in both wait-list groups and compare results to their PROM scores at the initial provider telemedicine visit and over time (6 months post first provider assessment). Consent may be in-person with hard copy consent forms and signatures or through e-Consent either in-person using ipads or remotely using REDCap.

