2. Randomly assign patient into group (REDCap will do this when you start a new patient record); inform patient of the group they have been randomly assigned into to provide further instructions.
3. Provide all patients with CONNECT phone number at termination of the call.

Initial consenting process occurs after routine clinical psychiatry intake assessment by intake coordinator (if intake coordinator assesses that patient has capacity to pursue study discussion): 30-45 min consent process through REDCap or hard copy in-person. REDCap will be utilized to perform randomization. There is no blinding due to the nature of the wait-list control groups; both patients and investigators will be aware of study group assignment.

No intervention group randomization: no additional time/study procedures occur after consent; **SO C monthly PROMs DO NOT begin until after initial psychiatric provider evaluation for 6 additional months.**

Minimal intervention randomization: each month PROMs including PHQ-9, GAD-7 and BASE-6 are sent automatically for subject to complete via email or cell phone before initial psychiatric provider appointment - takes approximately 15 minutes to complete; watching microlearning videos about illness/symptoms takes approximately 15-30 minutes to watch depending on # videos recommended. Current wait-time for patients to see MD provider is 3-4 months; therefore, subjects in the minimal intervention group will participate in the study for up to 6 months before beginning regular treatment with provider.

PROM data from both groups will continue at initial psychiatric provider evaluation and monthly as is current clinical practice. Therefore, an additional 6 months of PROM data for each group will be followed to assess the research question of whether a no intervention or minimal intervention group may provide benefits to patients waiting to be seen and followed by psychiatric providers.

Total study participation time = 6-12 months depending on length of wait time before first psychiatric provider appointment

You must attach surveys, instruments, interview questions, focus group questions, etc. in the Initial Submission Packet and label them clearly.

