 - Example: This IRB application is being submitted on 12/1/21 and the study is collecting data on a standard of care surgery and looking at patient outcomes. All surgeries for this prospective studies will be completed between 1/1/2022 and 1/1/2025. This study will require informed consent UNLESS a waiver of consent is requested and justified.

Attach a copy of your data collection tool or spreadsheet listing exactly what data is to be gathered during this research study.

The intake assessments beginning 10/25/21 are Standard of Care (SOC). This data would not be included in this proposed study/consent because only NEW patients being referred/assessed by the intake coordinator are part of the study. If patients have already been assessed and are waiting for a provider appointment they are not part of any study. This data between 10/25/21 and date of IRB approval for this study would be requested in an amendment should the investigators want to include this preliminary SOC data.

Data collection sheet source document attached to this application.

Psychiatry intake assessments began October 25, 2021.

This study, with randomization to wait-list control groups (no intervention vs minimal intervention), will begin once IRB approval and REDCap build has been completed - estimate by end of January 2022.

Retrospective data involving initial psychiatric intake and intake PROM completion scores beginning October 25, 2021 may be requested as a future amendment after approval of this study.

19.4 Describe how long individual participants will be actively in the study. If there will be a period of time after the active component of the study where participants will still be in the study (ex: participants outcomes are being extracted from the medical record at 1 year, but the last research study visit was at 3 months), state this as well.

Participants will be active in the study for 6-12 months - monthly PROMs will be collected for 6 months after initial psychiatric provider assessment in addition to wait-time prior to first appointment.

19.5 Describe how long the entire study is expected to last, including data analysis.

The entire study including data analysis will be two years (estimate 12.1.21-11.30.23 estimate based on date of IRB approval) - iTHRIV funding is approved for 2.1.22 to 1.31.23.

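### The six-month comparison of the randomised arms opens at the first provider visit, so it is conditional on attendance; label it supportive and report attendance and time to visit by arm

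*Combined protocol and SAP*

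**What the plan says.** Section 19.1 randomises at the end of intake: "Randomly assign patient into group (REDCap will do this when you start a new patient record". The provider visit comes later: "Current wait-time for patients to see MD provider is 3-4 months", and the section allows up to 6 months in the minimal-intervention arm before treatment begins. In the no-intervention arm, monthly PROMs "DO NOT begin until after initial psychiatric provider evaluation for 6 additional months". After the visit, "an additional 6 months of PROM data for each group will be followed to assess the research question", that question being whether either wait-list condition benefits patients who are waiting.

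Two other places set the same anchor. Section 10.5 plans to look at change during the wait in each arm. It will then "compare results to their PROM scores at the initial provider telemedicine visit and over time (6 months post first provider assessment". Section 19.4 says "monthly PROMs will be collected for 6 months after initial psychiatric provider assessment in addition to wait-time prior to first appointment".

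Section 10.7 takes change in total PROM score as the primary outcome, using the last PROM completed. Its t-test is worded as telemedicine patients against wait-list controls. It also plans trends by time in program, without saying when that time starts. It defines no analysis set and no rule for participants who never reach a provider. The aims in Section 10.6 concern symptoms and well-being, not attendance.

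Section 9.15 lists the fields that an external data manager will see. There the date of an assessment, apparently the intake assessment, "will be put as day 1 NOT a specific date of appointment".

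**The concern.** Randomisation protects a comparison of everyone assigned, counted from assignment. The post-visit window departs from this in two ways. A participant enters it only by attending the first provider visit, and the clock starts when that visit happens. If arm affects either one, the attenders in the two arms are no longer comparable, even if every attender completes every PROM.

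The documents give reasons to think arm might matter:

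- **Attendance.** Section 10.5 reports that measurement-based care lowers dropout, and repeated PROMs are part of what the minimal-intervention arm receives.
- **Timing.** Section 15.18 has the coordinator assess severity and safety at the monthly measurements, which only the minimal-intervention arm has while waiting. Section 23.5 moves a Tier 1 score to the top of the referral list. Read together, these allow an earlier visit in one arm. The script in Section 19.1 tells participants that taking part does not change the wait.

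If the minimal intervention keeps people in the pathway who would otherwise have left, and those people do worse, the arm that retains more will look worse after the visit.

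**Working it through.** **Plan's own figures.** There is no power, SD, effect size or attendance rate to reproduce. Section 11.2 gives 200 participants and Section 11.3 gives 100 in the no-intervention arm. The other arm is taken as 200 - 100 = 100.

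**Anchor and timing.** Section 19.1 states total participation of 6-12 months. A wait of 0-6 months plus 6 months after the visit gives 6-12, which confirms that the window is anchored at the visit. Time from randomisation to the end of the window is wait + 6:

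- 3-month wait: 3 + 6 = 9 months
- 4-month wait: 4 + 6 = 10 months
- 6-month wait: 6 + 6 = 12 months

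Six months after the visit is therefore not a common time since randomisation.

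**Bias from comparing attenders only.** Code the outcome so that higher is better, and suppose there is no true effect. Let p be attendance in an arm and δ the attender minus non-attender difference in SD units, the same in both arms. The attender mean is μ + (1 - p)δ. The minimal minus no-intervention difference is then biased by (p_C - p_M)δ, where C is no intervention and M is minimal intervention. The false-positive rate uses SE = √(1/(100p_C) + 1/(100p_M)) and two-sided alpha 0.05 (Section 10.7 gives 0.05 without sidedness). All attendance rates and δ values are assumptions.

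| Attendance, two arms | δ | Size of bias (SD) | SE | False-positive rate |
|---|---|---|---|---|
| 90% and 80% | 0.5 | 0.10 × 0.5 = 0.05 | 0.154 | 6.2% |
| 90% and 80% | 1.0 | 0.10 × 1.0 = 0.10 | 0.154 | 10.0% |
| 90% and 70% | 0.5 | 0.20 × 0.5 = 0.10 | 0.159 | 9.6% |
| 90% and 70% | 1.0 | 0.20 × 1.0 = 0.20 | 0.159 | 24.1% |

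If attendance and its causes are equal in both arms, the bias is 0 and the rate is 5%.

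**A second model as a check.** Suppose attendance depends on a normal propensity whose correlation with outcome is ρ. The size of the bias is ρ[φ(z(a₁))/a₁ - φ(z(a₂))/a₂], where a₁ and a₂ are the lower and higher attendance rates. For ρ = 0.3-0.7:

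- 70% against 80%: 0.04-0.10 SD, false positives 5.8-9.6%
- 60% against 80%: 0.09-0.21 SD, false positives 8.1-22.6%

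The two models agree on the order of magnitude.

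**The case against.** The strongest reply is that Sections 10.5, 19.1 and 19.4 describe when data are collected, not how they are analysed. Section 10.7 does not say that participants are aligned by visit date; time in program could start at intake, and Section 10.5 can be read as a within-person comparison. Aim 1, the waiting-period question, ends at the initial psychiatric session, before this window opens. This stands in part. Aim 1 is not affected, and the analysis origin is undefined rather than wrong. But Section 19.1 does use the post-visit data to judge the two arms, and those data exist only for attenders, apart perhaps from one bundle requested 24 hours before the appointment (Section 10.4).

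A reader might infer that the study's data cannot show who attended. The documents do not support that. Section 9.15 lists only the external data manager's view, and the data collection sheet is an attachment not available here.

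A reader might also infer that the plan's primary test has a false-positive rate of up to 24%. That is not supported either: the t-test in Section 10.7 is worded for a different contrast, and 24% needs both a 20-point attendance gap and a full 1 SD difference, neither of which the documents give. At the mild end, 6.2% is close to nominal.

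Nor can attendance and visit timing be treated as immune to repeated testing, because Sections 15.18 and 23.5 allow monthly scores to move the appointment. Attendance is also a weak test endpoint: with 100 per arm, power is 37% for 70% against 80%, and 88% for 60% against 80%. That argues for reporting it with a confidence interval, not for omitting it.

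**Conclusion.** The point holds for the post-visit phase. The six-month arm comparison in Section 19.1 is conditional on attending a visit that follows randomisation, and its window ends 9-10 months after randomisation at the stated wait, or up to 12. This follows from the plan's text alone.

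Whether it produces bias, and how much, is unknown. The range of 0 to about 0.20 SD rests on assumed attendance gaps of 0-20 points and an assumed attender/non-attender difference of 0.5-1.0 SD. Whether visit dates are already captured is also unknown. What is established is that the text defines no analysis set for this comparison, does not report attendance by arm, and leaves the time origin open. These should be settled before the comparison is read as a randomised one.

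**What to change.** In Sections 10.7 and 19.1:

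1. Take from the EMR whether the first provider visit took place and the days from randomisation to it. Report both by arm for all randomised, with confidence intervals. Note that time to visit may itself be changed by monthly triage scores.
2. For any comparison of the randomised arms, define time in program from randomisation and analyse by assigned arm. Use a repeated-measures model that takes every score already collected, with the intake score as one of the responses so that non-attenders stay in. State that their later scores are missing, that the model assumes they are missing at random, and add a sensitivity analysis. The assumption bears hardest on the no-intervention arm, whose non-attenders will normally have intake scores only, while minimal-intervention non-attenders may have monthly waiting-period scores.
3. Label the six-months-post-visit arm comparison as conditional on attendance and supportive only.

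Sections 15.18, 19.1 and 23.5 must also be reconciled on whether arm can change the wait; no clinical rule is proposed here.

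**Cost.** A small EMR extraction, supplied as days so that no date is shared; Section 20.1 now describes EMR review for the intake assessment only, so its wording needs extending. There is some extra analysis, and the post-visit comparison carries less weight. No new PROM collection is required, which matters because consented enrolment began on 4.6.22 (Section 13.3) and the form is dated 03/16/2023.

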 - Example: This IRB application is being submitted on 12/1/21 and the study is collecting data on a standard of care surgery and looking at patient outcomes. All surgeries for this prospective studies will be completed between 1/1/2022 and 1/1/2025. This study will require informed consent UNLESS a waiver of consent is requested and justified.

Attach a copy of your data collection tool or spreadsheet listing exactly what data is to be gathered during this research study.

The intake assessments beginning 10/25/21 are Standard of Care (SOC). This data would not be included in this proposed study/consent because only NEW patients being referred/assessed by the intake coordinator are part of the study. If patients have already been assessed and are waiting for a provider appointment they are not part of any study. This data between 10/25/21 and date of IRB approval for this study would be requested in an amendment should the investigators want to include this preliminary SOC data.

Data collection sheet source document attached to this application.

Psychiatry intake assessments began October 25, 2021.

This study, with randomization to wait-list control groups (no intervention vs minimal intervention), will begin once IRB approval and REDCap build has been completed - estimate by end of January 2022.

Retrospective data involving initial psychiatric intake and intake PROM completion scores beginning October 25, 2021 may be requested as a future amendment after approval of this study.

19.4 Describe how long individual participants will be actively in the study. If there will be a period of time after the active component of the study where participants will still be in the study (ex: participants outcomes are being extracted from the medical record at 1 year, but the last research study visit was at 3 months), state this as well.

Participants will be active in the study for 6-12 months - monthly PROMs will be collected for 6 months after initial psychiatric provider assessment in addition to wait-time prior to first appointment.

19.5 Describe how long the entire study is expected to last, including data analysis.

The entire study including data analysis will be two years (estimate 12.1.21-11.30.23 estimate based on date of IRB approval) - iTHRIV funding is approved for 2.1.22 to 1.31.23.

20.0 Research Review of Data/Records

20.1 What types of records will be reviewed for this research study?

- Medical record/medical chart
- Films/x-rays
- Data in a database
- Hospital administrative/billing records
- Quality improvement records
- Publicly available database
- Other

Provide a detailed description about your selection above, including if the records are already in existence at the time of this submission or if you will be accessing future records, and special permissions that may be needed to access the data/records:

EMR review for initial psychiatric intake assessment (part of routine care) with PHI elements put into REDCap for research purposes. Owl Insights is a cloud-based system that provides PROMs and is a database of PROM measures for the past 2.5 years in our ambulatory clinic. Over 100,000 individual PROMs have been completed to date by patients in ambulatory psychiatry.

20.2 What is the original purpose of the data being reviewed?

- Clinical Care
- Collected as part of routine business activities
- Research Study
- Collected under Repository Protocol
- Other

20.3 If collected as part of a previous research study or repository protocol, enter the IRB number for the study.

20.4 Is the data identifiable private information or Protected Health Information (PHI)?

- Yes
- No

21.0

Incidental Findings

21.1 Does this study involve any imaging procedures (x-rays, CT, MRI, PET, ultrasound, etc.) specifically for research purposes?

Yes No

21.2 Does the research include any of the following?

- Exams, blood tests, genetic tests or markers, or other tests or procedures that may generate incidental or secondary findings, including disease or conditions other than the one under study, or familial relationships including paternity and ancestry.
- Testing for communicable diseases
- None

22.0

Identification/Recruitment of Subjects

22.1 How do you plan to identify potential subjects?

To "identify" a potential subject refers to procedures to determine which individuals may qualify to participate in the study in order to decide which individuals to contact about taking part.

Check all that apply:

	
Existing Record Review, including Medical Chart Review, Clinic Schedule Review, or QA-QI Database Review.
	
Select all that apply:
 
  Patients' records reviewed will be those from research team's own patient population  Patients' records will be those from other physicians or medical practices' patient population 
* You must request Waiver of Informed Consent and, if any HIPAA identifiers are collected, a Waiver of HIPAA Authorization for recruitment purposes.

	
Researchers who ARE NOT treating clinicians of potential subjects will ask treating clinicians for referrals of eligible patients interested in the study.
	
Select all that apply:
 
  Treating clinicians will identify potentially eligible patients and obtain patient permission before providing researchers with patient contact information.  Treating clinician will provide documentation of patient permission in a email/letter to researcher, and researcher must

		document permission in research record.
		* You must request a Waiver of Informed Consent/HIPAA Authorization for recruitment purposes.
	Potential subjects will not be directly identified by the researchers from existing records. The potential subject will obtain IRB-approved information about the study from an advertisement, flyer, brochure, website, grand rounds presentation, department meeting, etc. In most cases, the potential subject will contact the researcher if interested.	Comments: _____
	Review of Registry/Database in which individuals have previously signed a consent giving their permission to be contacted for future studies.	Comments: _____
	Student Records	Comments: _____
	Other	Please specify other: _____

22.2 Please describe the identification process.

*List all information you plan to collect and record during the identification process **PRIOR** to contacting potential subjects. This includes the inclusion/exclusion criteria and demographics to determine if a person qualifies for a study before contacting that person to be a potential subject.*

No information will be collected specifically for the study prior to contacting the person.

The psychiatry intake coordinator will call all people referred to adult ambulatory psychiatry and complete an intake assessment. Once the assessment is completed, patients will be asked if they would like to participate in the wait-list study and be randomized to either a no intervention group (no further interaction between intake and first clinician appointment) or to minimal intervention group (patients will receive monthly reminders to complete PHQ-9, GAD-7 and BASE-6 and be assigned micro-learning videos to view during the wait-time for their first clinician appointment).

A waiver of informed consent/HIPAA authorization is requested for recruitment purposes only.

